10.3 Grading and Attribution of Adverse Events

10.3.1 Grading Criteria

The study site will grade the severity of adverse events experienced by the study subjects according to the criteria set forth in the National Cancer Institute's Common Terminology Criteria for Adverse Events (CTCAE V5.0). This document (referred to herein as the NCI-CTCAE manual) provides a common language to describe levels of severity, to analyze and interpret data, and to articulate the clinical significance of all adverse events. The NCI-CTCAE has been reviewed by the DAIT/NIAID Medical Monitor and has been deemed appropriate for the subject population to be studied in this protocol.

Adverse events will be graded on a scale from 1 to 5 according to the following standards in the NCI-CTCAE manual:

- Grade 1 = mild adverse event.
- Grade 2 = moderate adverse event.
- Grade 3 = severe and undesirable adverse event.
- Grade 4 = life-threatening or disabling adverse event.
- Grade 5 = death.

10.3.2 Attribution Definitions

For the purpose of this surveillance study, only AEs related to a study-mandated procedure will be reportable and by definition will always be assessed as related. The degree of certainty about relatedness will be graded using the 2 categories below.

Table 12.3.2 Attribution of Adverse Events

Code	Descriptor	Relationship (to study procedure)
RELATED CATEGORIES		
2	Possibly Related	The adverse event has a reasonable possibility to be related; there is evidence to suggest a causal relationship.
3	Related	The adverse event is clearly related.

10.4 Collection and Recording of Adverse Events

10.4.1 Collection Period

Adverse events will be collected from the time of first procedure, until a participant completes the study, until 48 hours after he/she prematurely withdraws, or is withdrawn from the study.

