6.2. Index participants and Household Contacts Study Assessments

6.2.1 Caregiver-Collected Samples

At the times shown in the Schedule of Events (Table A), the primary contact/caregiver will collect nasal swabs from the index participants and all family members that are enrolled in the study at the beginning of the study (Week 2) and every 2 weeks thereafter for 9 collections, then a final 10th nasal swab collected at the end of the study (total 10 nasal swabs collected over 24 weeks). If the household agrees to participate in the study extension, 4 additional nasal swabs will be collected between Week 18 and Week 28 (Table A). Stool samples via swabs will be collected from the index participants and all family members that are enrolled (starting at Week 2) into the study (Table A). Blood samples will be collected via the OnDemand device from the index participants and all family members that are enrolled in the study and 2 years of age and older (Table A). Nasal secretion and/or saliva samples may also be collected from the index participants and all enrolled family members at Week 24. Samples will be shipped as instructed in the sample kit package. Details of the nasal swab, stool collection, blood collection, nasal secretion, and saliva procedures will be provided in the sample kit package.

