6.4. Sample Collection/Questionnaire Completion Windows

Sample collection and completion of the study questionnaires should take place within the time limits specified in the Schedule of Events (Table A).

Table A. Schedule of Events for All Participants

*The window for sample collection and completion of Symptom and Exposure surveys is (+/-) 4 business days

¹There is no window for the baseline (Week 2) blood collection.

²Additional nasal swab and a stool samples will be collected when a household member shows signs of a viral illness and a study-specified threshold for symptom algorithm has been met. For the first illness, the nasal swab sample will be collected within 24 hours from all study participants, including the affected household member, and a stool sample from just the affected household member. Subsequent illnesses will be assessed only if the index participant is affected; in this case a swab and a stool sample will be obtained within 24 hours only from the index participant.

³A nasal secretion and/or saliva sample may be collected at End of Study.

⁴Nasal swabs will be collected at Week 20, 22, 26 and 28 and Health Check Surveys at Week 19, 21, 23, 25, and 27 from participants that agree to participate in the study extension.

⁵An end of study blood sample will be collected from all study participants that are at least 2 years old at Week 24 or at Week 28, if the participant decided to continue in the study with the original visit plan or agreed to participate in the extension, respectively.

⁶An additional blood sample will be collected from all study participants that are at least 2 years old three weeks after a first illness in the household and a study-specified threshold for the symptom algorithm has been met.

7. Laboratory Assays

- SARS-CoV-2 detection and nasal transcriptomics. RNA extracted from all swabs will be used to perform RT-qPCR for SARS-CoV-2. The remaining RNA and DNA will be stored for possible detection (and quantification) of other respiratory viruses, for generating the host transcriptome response to infection (from airway epithelial and any immune cells that were present on the nasal swab), and for delineating the nasal microbiome at the time the swab was collected.

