9.1. Participant Completion

Participation of the index participants, caregiver, and sibling(s) will be complete at Week 24 (original schedule of events) or Week 28 if the household agrees to the study extension.

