10.2 Definitions

10.2.1 Adverse Event

For this surveillance study, an adverse event (AE) is defined as any untoward or unfavorable medical occurrence in a participant that is associated with a study procedure mandated by the protocol and occurs within 48 hours of this procedure. This definition excludes all untoward or unfavorable medical occurrences not related to a study procedure, including hospitalizations or deaths. The study mandated procedures are listed in the Schedule of Events (Table A). Criteria for determining the relatedness of an AE to a study procedure and grading its severity are provided in Sections 10.3.1 *Grading Criteria* and 10.3.2 *Attribution Definitions*. The worsening of a participant's pre-existing medical condition will not be considered an AE unless the worsening is related to a study mandated procedure.

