10.4.3 Recording Adverse Events

Throughout the study, the clinical site investigators will record adverse events and serious adverse events as described previously (Sections 10.2.1, 10.2.2) on the appropriate AE/SAE eCRF

Once recorded, an AE/SAE will be followed until it resolves with or without sequelae, or until the end of study participation, or until 48 hours after the participant prematurely withdraws or is withdrawn from the study, whichever occurs first.

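### The stated adverse event collection period does not assure the 48-hour window after a completer's last study procedure

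*Combined protocol and SAP*

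**What the plan says.** Section 10.2.1 limits AEs to an event that "is associated with a study procedure mandated by the protocol and occurs within 48 hours of this procedure". Every procedure thus carries its own 48-hour risk window.

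Section 10.4.1 starts collection at the first procedure and runs it "until a participant completes the study, until 48 hours after he/she prematurely withdraws, or is withdrawn from the study". Section 10.4.3 follows a recorded AE to resolution, "or until the end of study participation, or until 48 hours after the participant prematurely withdraws or is withdrawn from the study", taking whichever comes first. In both places the 48 hours attach to withdrawal only.

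Section 9.1 says participation "will be complete at Week 24 (original schedule of events) or Week 28 if the household agrees to the study extension". Section 6.2.1 describes nine two-weekly swabs, "then a final 10th nasal swab collected at the end of the study (total 10 nasal swabs collected over 24 weeks". The footnotes to Table A (section 6.4) put a swab at Week 28 for households in the extension. They put the end-of-study blood sample, for participants aged 2 or older, at Week 24 or Week 28 according to the schedule followed. A nasal secretion or saliva sample may also be taken at the end of the study. On timing, Table A adds: "The window for sample collection and completion of Symptom and Exposure surveys is (+/-) 4 business days".

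Under section 10.4.2, AEs come to light through questions built into the study questionnaires or through unsolicited complaints.

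**The concern.** The AE definition and the collection period are not aligned at the end of participation. A person who withdraws is covered for 48 hours afterwards. A person who finishes, and may have had a lancet draw and a swab in the same week, gets no added time. The same pattern appears for collection and for follow-up, so it is not a slip in one sentence.

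The stake is procedure safety. Samples are taken at home, by caregivers. Section 5.1 lists discomfort and rare mild epistaxis for swabs, and syncope, discomfort and rare local infection for the blood device. Procedure-related events are the only AEs and SAEs the study reports, and the Medical Monitor's monthly review (section 10.6.1) is built from those records. An event that meets the definition after the last procedure could fall outside the period in which sites are told to collect it. An AE already recorded at that point could have its follow-up closed almost at once.

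**Working it through.** The plan gives no figure to reproduce on this point. The check sets the sections side by side and works out the uncovered time.

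**Inputs**
- AE window after each procedure: 48 hours (10.2.1).
- End of collection: study completion for completers; withdrawal plus 48 hours for others (10.4.1, with the same pattern for follow-up in 10.4.3).
- Completion: Week 24 or Week 28, stated only as a week (9.1).
- Last scheduled swab and blood draw: the same week (6.2.1 and Table A footnotes).
- Window for samples and for the symptom and exposure survey: 4 business days either side (Table A).
- Scheduled swabs: 10, or 14 in the extension (6.1, 6.2.1).
- Household size: 2 to 4 enrolled members; up to 2000 families (synopsis, 3.1).

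**Uncovered time.** Let P be the time of the last procedure and C the end of collection. The uncovered part of the window is U = 48 − (C − P) hours, held between 0 and 48.

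| Situation | C − P | U |
|---|---|---|
| Completer; completion dated at the final sampling | 0 h | 48 h |
| Completer; final sampling one day before a fixed completion date | 24 h | 24 h |
| Completer; final sampling at least 48 h before a fixed completion date | 48 h or more | 0 h |
| Completer; final sampling late in the window, after a fixed completion date | negative | 48 h |
| Withdrawn; last procedure at or before withdrawal | 48 h or more | 0 h |

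For completers U therefore ranges from 0 to 48 hours. For those who withdraw it is always 0.

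**Does a later contact close the gap?** Section 6.2.2 ties the symptom and exposure survey to the nasal sample. In the extension the last health check is at Week 27, before the Week 28 swab. The text describes no questionnaire scheduled after the final sampling.

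**Share of procedures.** The final swab is 1/10 = 10% of scheduled swabs, or 1/14 = 7.1% in the extension. I give no share for blood draws, because the body of Table A is not in the text available and illness-triggered draws vary by household.

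**People.** 2000 × 2 = 4000 and 2000 × 4 = 8000. This is the largest number who could have a final sampling. Participants who withdraw must be subtracted, since they already have the 48 hours, and children under 2 give no blood.

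**After the change.** If C is at least P + 48 hours for completers, then C − P is at least 48 and U = 0 in every row.

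**The case against.** The strongest reply is that the gap may often be small. Completion is given as a week, not as the moment of the last sample. If it is a fixed date, a family that samples early in the window has full cover. The last survey shares the sampling window, so it may be filled in after the last sample and pick up an event. An unsolicited complaint may still reach the site. Syncope and epistaxis would be expected at or near the procedure; of the listed risks, local infection is the one most plausibly delayed, and the protocol calls it rare. Safety is not among the primary, secondary or exploratory outcomes, and SAEs are described as very unlikely.

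Most of this stands, and it limits the size of the point. It does not remove it: none of these routes assures cover, and section 10.4.1 makes no provision for collecting a complaint that arrives after completion.

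A reader might infer more than the documents support:
- That events after the last procedure are simply not captured. The text shows only that the stated period does not assure capture.
- That the sections contradict each other. One defines an AE and the other sets how long AEs are collected; the second is narrower at the end of the study, which is a gap in coverage.
- That half of all scheduled draws lack a window. This applies the worst case to everyone, and assumes exactly two scheduled draws on the strength of footnotes alone.
- That 4000 to 8000 events or windows are lost. That is a ceiling on people, and the documents give no AE rate from which to estimate missed events.

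**Conclusion.** The point holds as a gap in assured coverage. Followed as written, sections 10.4.1 and 10.4.3 can leave 0 to 48 hours of a completer's last AE window outside collection and follow-up, while those who withdraw always have the full 48 hours. Where in that range a participant falls depends on two things: when in the sampling window the final sample is taken, and whether completion means the last sampling or a nominal date. The protocol does not settle the second.

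The effect is confined to the last procedures of completers. Earlier procedures are covered. The degree of under-reporting, if any, cannot be estimated from the documents. The incidence estimates and the sample size are not touched. It is a modest defect, but it lies in the only safety data the study collects and is nearly free to repair. The conclusion assumes that the body of Table A, which is not in the text available, schedules no contact after the final sampling.

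**What to change.** In sections 10.4.1 and 10.4.3, state that for completers AEs are collected and followed until study completion or 48 hours after the last study procedure, whichever is later. In 10.4.3 this replaces only the end-of-participation limit; follow-up still stops earlier if the event resolves.

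Keep the existing rule of 48 hours after withdrawal. A single rule of 48 hours after the last procedure for everyone would be simpler, but it would shorten cover for some. Someone who withdraws 14 days after the last sample is now followed to day 14 + 2 = 16; under the single rule follow-up would end at day 2.

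Send completers one closing AE question through the existing online system once the 48 hours have passed, so that the longer period has a means of detection.

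Cost: one sentence in each of two sections, one extra online question, and up to 48 hours more follow-up after the last procedure for completers.

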10.4.2 Collecting Adverse Events

Adverse events (including SAEs) may be discovered through any of these methods:

- Interviewing the participant through specific questions that will be incorporated in the study questionnaires
- Receiving an unsolicited complaint from the participant

10.4.3 Recording Adverse Events

Throughout the study, the clinical site investigators will record adverse events and serious adverse events as described previously (Sections 10.2.1, 10.2.2) on the appropriate AE/SAE eCRF

Once recorded, an AE/SAE will be followed until it resolves with or without sequelae, or until the end of study participation, or until 48 hours after the participant prematurely withdraws or is withdrawn from the study, whichever occurs first.

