10.2.2 Serious Adverse Event (SAE)

SAEs are very unlikely to occur and reportable SAEs for this surveillance study will be limited to those related to study procedures. An SAE is defined as an AE meeting 1 of the following conditions:

- Death.
- A life-threatening event: An AE is considered "life-threatening" if, in the view of either the investigator or the DAIT Medical Monitor, its occurrence places the subject at immediate risk of death. It does not include an AE that, had it occurred in a more severe form, might have caused death.
- Inpatient hospitalization or prolongation of existing hospitalization.
- Persistent or significant incapacity or substantial disruption of the ability to conduct normal life functions.
- Important medical events that may not result in death, be life threatening, or require hospitalization may be considered serious when, based upon appropriate medical judgment, they may jeopardize the participant and may require medical or surgical intervention to prevent one of the outcomes listed above.

Any other condition that, in the judgment of the investigator, represents a significant hazard, such as an important medical event that does not result in one of the above outcomes, may be considered an SAE when the event is related to a study procedure and jeopardizes the participant or requires medical or surgical intervention to prevent one of the outcomes listed above.

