10.6 Review of Safety Information

10.6.1 Medical Monitor Review

The DAIT/NIAID Medical Monitor will receive monthly reports from the Statistical and Clinical Coordinating Center (SACCC) compiling new and accumulating information on AEs and SAEs recorded by the study site(s) on appropriate eCRFs.

The DAIT/NIAID Medical Monitor will also assess whether a study stopping rule has been met and will recommend either halting of the study for review of the safety information or study termination.

11. Statistical Considerations and Analytical Plan

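### Section 10.4.3 stops following a recorded, unresolved AE or SAE at end of participation or 48 hours after withdrawal, so later worsening and final outcome may go unrecorded

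*Combined protocol and SAP*

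**What the plan says.** Section 10.4.3 sets three limits on the follow-up of an event already on the AE/SAE eCRF. The first two are resolution of the event and the end of the person's participation. The third applies to anyone who leaves early: follow-up runs "until 48 hours after the participant prematurely withdraws or is withdrawn from the study, whichever occurs first". The earliest of the three limits applies, to AEs and SAEs alike.

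The same 48 hours appears in two other places. Section 10.2.1 uses it to define an AE, as an event that "is associated with a study procedure mandated by the protocol and occurs within 48 hours of this procedure". Section 10.4.1 uses it for the collection period, which runs "until a participant completes the study, until 48 hours after he/she prematurely withdraws, or is withdrawn from the study".

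Section 10.2.2 lists the SAE criteria, among them death, inpatient hospitalization and "Persistent or significant incapacity or substantial disruption of the ability to conduct normal life functions". It also says "SAEs are very unlikely to occur and reportable SAEs for this surveillance study will be limited to those related to study procedures".

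Section 9.1 ends participation at Week 24, or at Week 28 for households in the extension. Footnote 5 to Table A places the last blood sample at that same week. Section 9.2 allows the investigator to end participation, and it terminates caregivers and siblings when the index participant is terminated.

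**The concern.** An onset window and an outcome window answer different questions. The first decides whether an event counts as caused by a study procedure. The second decides how long an event already accepted as related is watched. In Section 10.2.1 the 48 hours does the first job. In Section 10.4.3 the same length of time, counted from withdrawal, does the second.

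Several SAE criteria can be met days after onset. Section 5.1.2 lists local infection at the lancet site as a rare risk, and that kind of harm can evolve after it first appears. Section 10.2.1 requires an AE to occur within 48 hours of the procedure, so a later hospitalization may reach the record only through follow-up of the original event. Section 10.4.3 stops that follow-up.

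What is at stake is the completeness of the safety record in a study where families carry out swabs and lancet draws at home on adults and children, with blood taken from age 2 upward. If an event worsens after closure, its recorded grade and seriousness stay at the earlier level. If it resolves after closure, the recovery is missing too.

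**Working it through.** The plan states no figure on this point, so there is none to reproduce. The check is mainly of the text.

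**1. Does another section extend follow-up?** Section 10.1 requires prompt reporting of AEs classified as serious, but it does not keep an unresolved event open. Section 10.6.1 sends monthly reports of recorded events to the Medical Monitor, but it adds no data collection. Section 10.4.1 concerns which events are collected. None of them extends Section 10.4.3.

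**2. Who is cut off, and when?** I read termination under Section 9.2 as being withdrawn in the sense of Section 10.4.3.

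| Group | Basis | Open event closes | Outcome still obtainable? |
|---|---|---|---|
| Completer, event from the last procedures | 9.1; Table A footnote 5 | Week 24 or 28, no tail stated | Yes, nothing was refused |
| Withdrawn by the investigator | 9.2 | 48 hours after withdrawal | Usually |
| Household contact terminated with the index participant | 9.2 | 48 hours after withdrawal | Often |
| Withdraws from all future activities | 9.2 | 48 hours after withdrawal | Only if contact is accepted |
| Lost to follow-up | 9.2 | 48 hours after withdrawal | No, under any rule |

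Completers get less time than withdrawers. Under Section 10.4.1, collection for completers also ends at completion. An event from the last draw can therefore fall inside the 48-hour onset window of Section 10.2.1 and outside the collection period.

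**3. A worked timeline.** The 48 hours run from withdrawal, not from the procedure. Take a draw on day 0 and a hospitalization on day 4.
- Onset and withdrawal on day 1: follow-up ends on day 1 + 2 = day 3, and the hospitalization is missed.
- Onset and withdrawal on day 2: follow-up ends on day 2 + 2 = day 4, and the hospitalization may be captured.

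The loss depends on timing and does not occur in every case.

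**4. Can the affected group be identified?** Assume equal AE risk at each of v visits, no attrition and the same chance of being unresolved at cut-off. The last visit then holds 1/v of AEs, and earlier visits hold (v − 1)/v. Let q be the share of earlier AEs that lead to withdrawal. Harm-related withdrawals outnumber last-visit events only if q(v − 1)/v > 1/v, that is, q > 1/(v − 1).

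| Procedures | v | Last-visit share 1/v | Break-even q = 1/(v − 1) |
|---|---|---|---|
| Swabs, original schedule (6.2.1) | 10 | 10.0% | 1/9 = 11.1% |
| Swabs, extension (6.1) | 14 | 7.1% | 1/13 = 7.7% |
| Baseline and end-of-study draws (Table A footnotes) | 2 | 50.0% | 1/1 = 100% |

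The documents give no value for q, so the dominant group cannot be named.

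**5. Can a count be given?** Section 3.1 enrolls 2 to 4 members in each of about 2000 families: 2000 × 2 = 4000 to 2000 × 4 = 8000 participants. Two scheduled draws each give at most 4000 × 2 = 8000 to 8000 × 2 = 16,000 draws, fewer once children under 2 are excluded, and before any draw after a first illness. The documents give no AE rate to apply to these denominators.

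**The case against.** The strongest case on the other side is that the short tail is a reasonable choice. This is observational surveillance with swabs and capillary blood. Only procedure-related events are reportable, and the protocol expects SAEs to be very unlikely. Participants who leave all future activities may not want contact. The 48-hour tail in Section 10.4.3 agrees with Section 10.4.1, so the two do not contradict each other for withdrawers. Section 10.2.2 lets the investigator class an important medical event as serious on judgment, without waiting for hospitalization. All of this stands, and it lowers the weight of the point. It does not cover completers, participants withdrawn by the investigator or household contacts terminated with the index participant. For these groups the rule itself, rather than a refusal, can end the follow-up.

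A reader might infer three stronger claims, and the documents support none of them.

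- **The loss falls mainly on people who withdraw because of the harm.** No reasons for withdrawal or AE rates are given, and step 4 leaves the question open. If AEs came only from the two scheduled draws, harm-related withdrawals could not outnumber events after the last draw.
- **The Medical Monitor sees events too late.** Section 10.1 requires prompt reporting of events classified as serious, and a closed record still appears in the monthly report. The interval between reports says nothing about how much outcome data are lost.
- **The stopping assessment is biased toward safety.** The rules in Section 9.4 are major new risks or doubtful feasibility, with no count or rate that a missing outcome would shift. Section 11 plans no safety endpoint or safety comparison.

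**Conclusion.** The point holds as a gap in safety data capture. Applied as written, Section 10.4.3 can leave worsening, a change in seriousness and the final outcome of a recorded event off the file, for completers as well as for people who leave early. This conclusion rests on the text alone. It assumes only that sites follow the rule literally and that some recorded events are unresolved at exit.

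Its size cannot be determined from the documents. A reader might assume that 1 in 10,000 to 1 in 1000 draws causes an AE that leads to withdrawal and outlasts follow-up. Applied to 8000 to 16,000 draws, that gives 0.8 to 16 events, but the result only restates the assumed rate and leaves out completers and swabs. The primary incidence estimate is unaffected. This is a cheap improvement of minor weight.

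**What to change.** In Section 10.4.3, state the two windows separately:

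- Keep 48 hours as the onset rule of Section 10.2.1.
- Keep every recorded SAE, and any AE unresolved at withdrawal or end of participation, open on the AE/SAE eCRF until it resolves, stabilizes or ends in death, unless the participant declines further contact.
- Allow grade and seriousness to be updated while the event is open.
- Carry open events forward in each monthly Medical Monitor report.
- Reconcile Sections 10.2.1, 10.4.1 and 10.4.3, including for events from the Week 24 or Week 28 procedures, so that completers are not left with less time than withdrawers.

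The cost is a short text change and a few contacts after participation ends, some of which will be declined. The change concerns data capture only and leaves study procedures and clinical care as they are.
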